- The number, n (%), of samples below the limit of quantification (LOQ), as defined per the laboratory protocol, will be calculated.
- The number, n (%), of samples below the limit of detection (LOD) will be calculated.
- Only PFAS (or summarized variables) with a detection rate >70% at baseline will be included in the statistical analysis [14, 15].

For values below the LOD, a common imputation approach will be used where concentrations are replaced by LOD/2 (i.e., one-half the detection limit). Sensitivity analyses may be conducted to evaluate the choice of imputation method for values below the LOD (e.g., LOD/2, LOD/ $\sqrt{2}$, or exclusion of values below the LOD) to assess the robustness of the imputation strategies.

Branched isomers of PFHxS, PFHpS, PFOS, PFNS, PFDS, and PFOSA will be calculated as:
Branched = sum – linear.

The difference in PFAS concentrations within each group from baseline at W1 to the end point at W18 between the study groups will be estimated using generalized linear models (or similar methods). For continuous outcomes, we will use an identity link function and assume a Gaussian distribution family.

We will also consider analyses using other distribution families based on the skewness of the data, as well as whether to categorize (e.g., dichotomize) the outcome variable.

We will also consider quantile regression and express the effects as the median differences between the study groups.

Bootstrap confidence intervals (95%) for median concentrations and median changes will be calculated using 1,000 resampling iterations to provide robust estimates that are not sensitive to non-normality.

We will also use mediation analyses to estimate the extent to which the effect is mediated through changes in albumin concentration.

Results

Figures

Flow chart of participants and samples, including ITT and PP populations and the number of donations.

Plots showing the concentration of different PFAS from week 1 to week 18.

Tables

Table 1: Baseline characteristics

	HFPDs	RFPDs	Control group
Age			
Height			
Weight			
BMI			
Donation history			
• Plasma			
• Whole blood			
Occupation			

Table 2: Baseline concentration of PFAS (incl. branched and linear isomers)

	HFPDs	RFPDs	Control group
PFBA (ng/mL)			
...			

Table 3: Concentrations of PFAS at W18 and change from W1

PFAS	HFPDs		RFPDs		Control group	
	W18	W18-W1	W18	W18-W1	W18	W18-W1
PFBA (ng/mL)						
...						

*p-value compared to controls at W18

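### For PFAS with incomplete detection, the baseline-only >70% rule plus LOD/2 substitution can make the planned W18 medians, median changes and bootstrap intervals reflect the substitution constant, most of all in HFPD

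*SAP*

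**What the plan says.** All of this is in the SAP, Statistical Analysis, unless another place is named.

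- **Entry:** "Only PFAS (or summarized variables) with a detection rate >70% at baseline will be included in the statistical analysis". There is no condition on W18 or on single arms.
- **Non-detects:** "For values below the LOD, a common imputation approach will be used where concentrations are replaced by LOD/2". No censored-data method is named, and nothing says how to report a median that lies below the LOD.
- **Checks:** "Sensitivity analyses may be conducted to evaluate the choice of imputation method for values below the LOD". The options listed are LOD/2, LOD/√2 or leaving the non-detects out.
- **Medians:** "Bootstrap confidence intervals (95%) for median concentrations and median changes will be calculated using 1,000 resampling iterations to provide robust estimates". This is a firm commitment. Table 3 has W18 and W18-W1 columns for each arm, and non-normal data are to be summarised by medians.
- **Models:** "For continuous outcomes, we will use an identity link function and assume a Gaussian distribution family". Quantile regression is softer: "We will also consider quantile regression and express the effects as the median differences between the study groups".
- **Transparency:** Table S2 (Supplementary) gives detection frequencies by arm at W1 and W18. Table S1 gives the range, median and mean of individual LODs.

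**The concern.** The entry rule looks at the visit before any donation, while the outcome is the change to a visit after which values should be lower. HFPD gives 24 × 0.65 L = 15.6 L of plasma, RFPD 8 × 0.65 L = 5.2 L, and controls two whole-blood donations. If donation lowers PFAS, the share of placeholders at W18 rises most in HFPD.

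With a single LOD, substitution distorts a change score in two ways. A donor below the LOD at both visits is recorded as unchanged, which pulls the median change towards zero. A donor who crosses the LOD is recorded as dropping straight to LOD/2, which overstates the fall unless the true value is already that low. The balance depends on the size of the fall, so the error differs between arms. The bootstrap resamples the placeholders as if they were measurements, so its interval does not show the problem. At stake are individual Table 3 entries for the affected PFAS.

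**Working it through.** The SAP gives no LODs, spread, expected fall or power figure, so there is no figure on this point to reproduce. Its donation volume does check: 720 × 56/(56 + 6) = 650 mL.

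**Assumed inputs.** Lognormal concentrations with W1 median 1; log-SD s = 0.4, 0.6, 0.8; W1 detection p = 72%, 90%, 99%; proportional falls f of 10-50%; within-donor variation 10%; one LOD per PFAS unless stated.

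**Are such falls plausible?** In a one-compartment washout with no new intake or elimination, the fall is 1 − (1 − 0.65/V)^24. For an assumed V of 30, 20 and 15 L this gives 41%, 55% and 66% in HFPD. With 8 donations and V from 30 to 15 L it gives 16-30% in RFPD. This shows plausibility only; it is not a forecast.

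**Formulas.** LOD = exp(−z_p·s). W18 detection = Φ[(z_p·s + ln(1 − f))/√(s² + 0.1²)]. The W18 median becomes LOD/2 once f exceeds 1 − exp(−z_p·s).

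**Base case, p = 72%, s = 0.6.** z = 0.583, LOD = exp(−0.350) = 0.705, LOD/2 = 0.35. The median reaches the floor at f = 1 − 0.705 = 30%. At 90% W1 detection that point is 1 − exp(−1.282 × 0.6) = 54%; at 99% it is 1 − exp(−2.326 × 0.6) = 75%. Median changes come from 400,000 simulated W1/W18 pairs per scenario:

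| True fall | Detected at W18 | True W18 median | Reported W18 median | Median change |
|---|---|---|---|---|
| 10% | 66% | 0.90 | 0.90 | 23% too small |
| 20% | 58% | 0.80 | 0.80 | 19% too large |
| 35% | 45% | 0.65 | 0.35 | 32% too large |
| 50% | 29% | 0.50 | 0.35 | 25% too large |

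**Range over s = 0.4-0.8:**

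| W1 detection | LOD | Fall | Error in median change |
|---|---|---|---|
| 72% | single | 35-50% | 20-39% too large |
| 72% | single | 10% | 16-30% too small |
| 72% | varying (log-SD 0.3) | 35-50% | about 9-19% too large |
| 90% | single | 35-50% | about 5-25% too large |
| 99% | single | 35-50% | 0-8% too large |

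The median change can be wrong while the W18 median is still a real measurement. At 80% W1 detection, log-SD 0.7 and a 30% fall, about 63% are detected at W18, yet the change is −0.619 against a true −0.501 (LOD units; 0.619/0.501 = 1.24).

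**Mean change, the target of the GLM, p = 72%.** Substituted over true is 0.98-1.04 at log-SD 0.6-0.8, and up to about 1.15 at 0.4.

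**Bootstrap.** 96 + 122 = 218 samples; 218/6 = 36.3, so 36 complete donors per arm are assumed. In the base case with a 35% fall, the nominal 95% interval for the median change covers the truth 48% of the time, against about 94% without censoring. With a 50% fall, the interval for the W18 median covers 29% of the time and has zero width in about 70% of simulated trials.

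**The listed checks.** At 90% W1 detection, log-SD 0.5 and within-person log-SD 0.15, in LOD units:

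| Fall | True | LOD/2 | LOD/√2 | Non-detects excluded |
|---|---|---|---|---|
| 30% | −0.536 | −0.643 | −0.577 | −0.652 |
| 50% | −0.931 | −1.099 | −0.990 | −1.336 |

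LOD/√2 reduces the error without removing it. Exclusion is worse than LOD/2.

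**The case against.** Much of the case on the other side stands.

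- **Conditional, not certain.** A reader might infer that the HFPD median change is misstated. The SAP gives none of the inputs that decide this, and the direction is not fixed. The figures at 72% detection sit just above the entry cut-off.
- **Primary outcomes.** A reader might infer that these are compromised. The Background reports linear PFHxS, both forms of PFOS, linear PFOA and PFNA in every sample of a Swedish blood-donor study. Near full detection the error is 0-8%. The exposure lies mainly among the 20 secondary PFAS and the isomer variables.
- **The committed model.** The Gaussian GLM compares means, which substitution barely moves in most scenarios. A biased median difference between groups would arise in quantile regression, which is only under consideration.
- **The word robust.** The SAP ties it to non-normality. It makes no claim about censoring.
- **Controls.** They are not free of placeholders: at 72% detection, 28% of every arm is at LOD/2 at W1. What differs is how that share grows.
- **Single LOD.** Table S1 suggests that LODs vary. With an assumed LOD log-SD of 0.3 and s = 0.6, the W18 median after a 35% fall is 0.55 against a true 0.65, the overstatement drops from 32% to 19%, and the 10% fall becomes a 20% overstatement.
- **Existing safeguards.** Table S2 would reveal heavy W18 non-detection, and the imputation checks might be run. Neither corrects an estimate, and no action follows from Table S2.

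Choosing PFAS on W1 alone is itself sound, because it avoids selecting on a post-randomisation result.

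**Conclusion.** The point holds in a limited form. Following the SAP as written can put wrong medians, median changes and intervals into Table 3 for PFAS with incomplete detection, with the largest risk where the fall is largest. The size ranges from negligible near full detection to about 20-39% in the median change just above the cut-off with one LOD, or about half that with varying LODs. These sizes rest on assumed lognormal spread, detection rates and falls, and should be read as a range. The documents do not support the stronger readings that the primary comparisons are unsound or that the main model is materially biased. This is a cheap improvement, not a flaw that undermines the trial.

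**What to change.** Keep the W1 entry rule and add two sentences to the SAP:

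1. *Where 50% or fewer samples in an arm-by-visit cell are detected, Table 3 gives the median as <LOD and shows no LOD/2-based median change or bootstrap interval for that arm.*
2. *For every included PFAS with more than 5% non-detects at W1 or W18, pooled over arms, a left-censored regression (Tobit or interval regression on log concentration, with sample-specific LODs and both visits treated as possibly censored) is reported for the group comparison alongside the LOD/2 result.* This replaces the optional comparison of substitution constants.

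The second sentence is needed because the median change can be off while more than half of the cell is detected.

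A trigger of W18 detection below 70% in any arm would be a poor choice. With true detection of 72% and no effect, one arm of 40 falls below 70% with probability 0.316, so at least one of three does with probability 1 − 0.684³ = 68%. For arms of 36 the figures are 0.428 and 1 − 0.572³ = 81%.

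Cost: two SAP sentences and a censored-regression fit in Stata. Table S2 already requires the detection counts. The affected PFAS take on a lognormal assumption and a ratio-scale estimate beside the ng/mL change, and some Table 3 cells will read <LOD.

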The plasma samples were centrifuged at 2200×g for 10 min immediately after collection, transferred into aliquots of 500 µL, and frozen at -40°C within 3 hours after collection. Within 3 months of storage, the samples were transferred to storage at -80°C until analysis. The samples were shipped on dry ice to the laboratory for analysis. PFAS analyses were conducted at the Environmental Pollutant Laboratory, University Hospital of North Norway, Tromsø, Norway, according to the method described by Huber and Brox [12]. Samples were analysed in two batches of 96 samples in 2023 and 122 samples in 2024.

Variables

Outcome Measures

Difference in plasma concentrations between W1 and W18 of the following PFAS:

Primary outcomes:

- Perfluorooctanoic acid (PFOA)
- Perfluorooctane sulfonic acid (PFOS)*
- Perfluorohexane sulfonic acid (PFHxS)*
- Perfluorononanoic acid (PFNA)
- Sum of PFOA, PFOS, PFHxS and PFNA [13]

Secondary outcomes:

- Perfluorobutanoic acid (PFBA)
- Perfluoropentanoic acid (PFPeA)
- Perfluorohexanoic acid (PFHxA)
- Perfluoroheptanoic acid (PFHpA)
- Perfluorodecanoic acid (PFDA)
- Perfluoroundecanoic acid (PFUDA)
- Perfluorododecanoic acid (PFDaDA)
- Perfluorotridecanoic Acid (PFTrDA)
- Perfluorotetradecanoic acid (PFTeDA)
- Perfluorobutane sulfonic acid (PFBS)
- Perfluoropentane sulfonic acid (PFPS)
- Perfluorooctane sulfonic acid (PFHpS)*
- Perfluorononane sulfonic acid (PFNS)*
- Perfluorodecane sulfonic acid (PFDS)*
- Perfluorodecane sulfonic acid (PFDaDS)
- Perfluorooctane sulfonamide (PFOSA)*
- 4:2 Fluorotelomer sulfonic acid (4:2 FTSA)
- 6:2 Fluorotelomer sulfonic acid (6:2 FTSA)
- 8:2 Fluorotelomer sulfonic acid (8:2 FTSA)
- 10:2 Fluorotelomer sulfonic acid (10:2 FTSA)

*Analysed as linear and branched isomers, and the sum of these.

Other variables:

- Plasma albumin concentration (as a mediator)

Independent Variables

- Study group identity (HFPDs, RFPDs, control group)

Statistical Analysis

Stata (StataCorp, College Station, TX, USA) will be used for the statistical analyses.

Outcome variables will be checked for normality. Normally distributed data will be expressed as mean (SD), and non-normally distributed data will be expressed as median (min-max and/or IQR). 95% confidence intervals will be used, and a two-tailed p-value < 0.05 will be considered statistically significant.

Samples below the detection and quantification limits:

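### The Gaussian model of change is not named primary, open alternatives could replace it, and the measured W1 concentration is not a covariate

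*SAP*

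**What the plan says.** Under Variables, Outcome Measures, the SAP defines the outcomes as W1 to W18 differences. PFOA, PFOS, PFHxS, PFNA and their sum are primary. The Independent Variables list has one entry: "Study group identity (HFPDs, RFPDs, control group".

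Under Statistical Analysis, the difference "will be estimated using generalized linear models (or similar methods". The default for outcomes on a continuous scale is stated next: "we will use an identity link function and assume a Gaussian distribution family". The team will then also consider "other distribution families based on the skewness of the data, as well as whether to categorize (e.g., dichotomize) the outcome variable". A further sentence reads "We will also consider quantile regression and express the effects as the median differences between the study groups". Bootstrap 95% intervals are planned for median concentrations and median changes.

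The sensitivity label is used for the detection-limit choices ("Sensitivity analyses may be conducted to evaluate the choice of imputation method for values below the LOD") but not for any of these modelling options. The footnote to Table 3 attaches the p-value to a comparison with controls at W18, although the table also has a column for change and the declared outcome is the change.

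The SAP is dated 01.09.2025. Blood Samples and Analyses places the two laboratory batches in 2023 and 2024. Timeline and Responsibilities puts SAP approval and data set completion in August 2025 and the statistical analysis in September 2025.

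**The concern.** The options do not estimate the same quantity. The Gaussian model gives a mean difference in change, quantile regression a median difference, and dichotomisation a contrast of proportions that depends on a cut-point nobody has set. The same data can be significant under one and not under another, and the plan does not say which result counts. A family chosen on observed skewness, or a decision on whether to categorise the outcome, reads more like choosing the analysis than adding a robustness check. With laboratory results complete before the plan's date, that choice could be made with data in hand.

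Separately, the W1 concentration has been measured and helps to predict the change, yet it is not listed as a covariate. Precision is lost, and whether to add it later is left open.

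**Working it through.** The plan gives no figure on this point, so there is none to reproduce.

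**Text**

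| Item | Fixed | Left open |
|---|---|---|
| Model class | Generalised linear model | Unnamed similar methods |
| Family and link | Gaussian, identity | Other families on skewness, no threshold, none named |
| Form of outcome | W1 to W18 difference | Dichotomised or not, no cut-point |
| Effect measure | Mean difference (implied) | Median difference |
| Covariates | Study group only | W1 not listed |
| Status of results | None labelled primary | Which result counts |

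**Inputs.** From the SAP: two-sided 0.05; 120 randomised 1:1:1; 96 + 122 = 218 samples, so at most 218/2 = 109 pairs, and 109/3 ≈ 36 per arm. Assumed, because the SAP gives no effect size or SD: 10% vs 2% reduction; W1 lognormal with log-SD 0.6 (range 0.4-0.8); change SD 0.15 (range 0.10-0.20), either proportional to the donor's level or constant in ng/mL (as a share of median W1). Each simulation covers one PFAS and one two-arm contrast, with 10,000 trials per scenario (Monte Carlo SE 0.5 points near 50%).

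**W1 as covariate.** With equal variance σ² at both visits and correlation ρ, the variance is 2σ²(1−ρ) for the unadjusted change and σ²(1−ρ²) after adjustment. The ratio is (1+ρ)/2: 0.75 at ρ = 0.5, 0.90 at 0.8, 0.95 at 0.9. The SAP's Background gives half-lives of 1-5 years, so a high ρ over 18−1 = 17 weeks is plausible and the expected gain is small. Simulated power (%), unadjusted → W1-adjusted:

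| Log-SD, change SD | Proportional scatter | Constant scatter |
|---|---|---|
| 0.6, 0.15 | 50.4 → 51.7 (+1.3) | 70.9 → 72.6 (+1.7) |
| 0.6, 0.10 | 82.0 → 85.5 (+3.5) | 94.4 → 96.1 (+1.7) |
| 0.6, 0.20 | 32.0 → 32.1 (+0.1) | 48.8 → 48.9 (+0.1) |
| 0.4, 0.15 | 58.5 → 59.1 (+0.6) | 65.9 → 65.9 (0.0) |
| 0.8, 0.15 | 42.1 → 44.6 (+2.5) | 75.4 → 80.8 (+5.4) |

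The plan's inclusion rule ("Only PFAS (or summarized variables) with a detection rate >70% at baseline will be included in the statistical analysis") admits up to just under 30% non-detects. With 5-29% non-detects at W1 and the planned substitution ("concentrations are replaced by LOD/2"), the gain is 1.0 to 2.8 points. Type I error of the adjusted model is 4.6-5.4%. A separately coded run of the first row gave 46.0 → 47.7 and 70.7 → 72.4, a gain of 1.7 points in both.

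**Can the choice change the verdict?** Share of trials in which the Gaussian model and a median split disagree on significance:

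| Assumed reduction, vs 2% | Proportional | Constant |
|---|---|---|
| 10% | 26.9% | 30.8% |
| 20% | 6.0% | 3.8% |
| 25% | 1.0% | 0.6% |

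Further runs of the 10% case gave 28-30%. Disagreement is common when power is moderate and rare when the effect is large.

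**Which analysis is stronger?** It depends on data features that the plan does not describe.

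- Normal scatter, base case: Gaussian 50.4% vs split 38.2% (proportional); 70.9% vs 43.4% (constant).
- Heavy-tailed t(3) scatter with the SD kept at 0.15: Gaussian about 57% vs split about 67% (proportional; another run gave 55.2% vs 66.2%); 76.7% vs 73.3% (constant).
- W1-adjusted log model vs W1-adjusted Gaussian: 65% vs 52% with proportional scatter and full detection; 47% vs 52% at 10% non-detects; 30% vs 73% with constant scatter.

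In the heavy-tailed proportional case W1 adjustment still helps: 55.2 → 57.2, and 47.6 → 51.5 at log-SD 0.8.

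**The case against.** The strongest reply is that the plan does fix a default. The Gaussian model is what the team will use, and the rest is only what it will also consider. On that reading, all that is missing is a label. This largely stands, and it is why the point is about wording and not a flawed analysis. It does not remove the point: the reference to similar methods loosens the default itself, and the sensitivity label that the SAP uses for the detection-limit choices is absent here. Choosing the model is also the SAP's own task, and this SAP takes it up, so it is not a matter left to the protocol.

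Second, a change score already uses W1, and an unadjusted comparison of randomised groups is unbiased. Both are true. What remains is a small gain in precision from data already collected.

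Third, the effect size behind the simulations is assumed and drives the disagreement rate. That stands, so the rate is shown at more than one effect size. A between-group bootstrap test of medians is left out of that comparison because the plan's bootstrap intervals are for median concentrations and changes and define no such test.

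Finally, a reader might infer from the dates that the options were left open after results had been compared by group. The SAP does not support this. It schedules the analysis for September 2025, and finished laboratory work shows opportunity only.

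**Conclusion.** The point holds as a specification weakness that should be corrected. The plan names a sensible default but does not make it decisive, and it leaves a measured covariate unused. W1 adjustment is worth about 0 to 5 power points under the stated assumptions, with type I error near 5%. The open choice can matter more, but only conditionally: about 28-30% disagreement between the Gaussian model and a median split at 10% vs 2%, about 4-6% at 20% vs 2%.

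Three stronger readings are not supported:

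- **That dichotomising always costs power.** It does under normal scatter in the base cases, but the split can win with heavy-tailed proportional scatter. The case against it here is the missing cut-point and the unstated status of its result.
- **That error inflation has a known bound.** Taking any of three tests (Gaussian change, median split, bootstrap median difference) gave 6.3-8.7% under the null, but that leaves out other families and cut-points. A separate calculation (log-SD 0.6, W1 to W18 correlation 0.8-0.95) gave about 10-11% with a log-scale test and one fixed cut-point, and 14-16% with three cut-points. All of these require selection by result, which nothing in the SAP shows.
- **That the Gaussian model is the most powerful choice.** The log model comparison shows otherwise in some settings. The reason to keep the Gaussian model is that the plan already commits to it and it preserves the declared ng/mL difference.

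**What to change.** In Statistical Analysis and Independent Variables:

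1. Name the Gaussian identity-link group contrast in W18−W1, adjusted for W1 concentration, as the single primary analysis for each primary outcome, and list W1 concentration as a covariate.
2. Remove the reference to similar methods. Label other families, a log-scale model, quantile regression and the bootstrap median intervals as supportive analyses that cannot replace the primary result.
3. Restrict the log-scale model to outcomes with all values positive and near-complete detection. Branched isomers are obtained by subtraction, so a logarithm may be undefined for them.
4. Drop dichotomisation, or fix its cut-point in advance and label it supportive.
5. State that the Table 3 p-value comes from the primary model of change and not from a comparison of W18 values alone.

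This costs SAP wording only. W1 is already measured, and the declared outcome is unchanged. The change settles which model counts for each outcome; it does not address multiplicity across the five primary outcomes and the group comparisons.

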Statistical Analysis Plan (SOP)

Parent study Title: “The Effect of Plasma Donation Frequency on Plasma Protein Composition, Inflammation Markers and Psychological Distress - a Randomized Controlled Trial”

Sub Study Title: “The Effect of Plasma Donation Frequency on PFAS Concentrations – a randomized controlled trial”

ClinicalTrials.gov Reference: NCT05179200

Date: 01.09.2025

Introduction

Background and Rationale

Poly- and perfluoroalkyl substances (PFAS) are synthetic compounds used for their water- and fat-repellent properties in products such as textiles, food packaging, cosmetics, and electronics [1-3]. PFAS are highly persistent in the environment and the human body, with long biological half-lives of 1-5 years [4]. As a result, they are widely detected in drinking water, soil, and food. Exposure in humans primarily occurs through the ingestion of contaminated water and food, as well as through everyday consumer products such as non-stick cookware, water-repellent clothing, food packaging, dental floss, and cosmetics. PFAS are absorbed into the bloodstream and bind to proteins rather than fat [3, 5-7], leading to bioaccumulation over time [1, 8]. This accumulation has been linked to adverse health effects, including immune suppression, hormonal disruption, elevated cholesterol, and potential carcinogenicity [9].

PFAS exposure is primarily assessed through blood concentrations. A recent Swedish study investigated PFAS exposure in the general population and analysed samples from 60 blood donors [10]. They detected 26 of 30 different PFAS and observed PFHxS-lin, PFOS (linear and branched), PFOA-lin, PFNA, and PFDA in all samples, and found the highest concentrations of PFOS-lin, PFOS-br, PFOA-lin, and PFHxS-lin.

A previous RCT in Australian firefighters, with high exposure to PFAS through firefighting foams, demonstrated reductions in PFAS concentrations following plasma donations every 6 weeks and blood donations every 12 weeks [11].

In this study, we aim to investigate the effect of different plasma donation frequencies on PFAS concentrations in blood donors.

Objectives

To compare the plasma concentration of different PFAS at baseline and after 16 weeks of donations between high-frequency plasma donors (HFPDs), donating plasma 3 times every 2 weeks, regular-frequency plasma donors (RFPDs), donating plasma once every 2 weeks, and a control group (controls) donating whole blood every 3 months.

Study Methods

Trial Design

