This is a randomized controlled trial, parallel-group, where 120 male blood donors were randomized 1:1:1 for donation over 16 weeks to:

- High-frequency plasma donors (HFPDs) donating plasma 3 times every 2 weeks (in total 24 times)
- Regular-frequency plasma donors (RFPDs) donating plasma once every 2 weeks (in total 8 times)
- The control group (controls) donating whole blood every 3 months (in total 2 times)

The study was conducted at the Blood Centre of Innlandet Hospital Trust from January 2022 to July 2024.

Trial Population

Established male blood- and plasma donors aged between 18 and 64 years were screened for eligibility. The inclusion criteria were sufficient levels of Hb, TSP, and IgG, an estimated blood volume (EBV) of at least 4500 mL, a donation history of at least one previous plasma donation, and the donors had to meet the eligibility criteria for both whole blood and plasma donation by plasmapheresis. Donors with a history of repeated measurements (>2) of haematocrit >50 % before enrolment were excluded.

All participants provided written informed consent. The study was approved by the Regional Committee for Medical and Health Research Ethics in Southeast Norway (2021/238929/REC Southeast A) and was conducted in accordance with the Declaration of Helsinki. The study is registered at clinicaltrials.gov (identifier: NCT05179200).

Intervention

The plasmapheresis procedure was performed using the Aurora Plasmapheresis machine, Fresenius Kabi. The plasma donation volume was 720 mL, including AC, which corresponds to approximately 650 mL plasma, excluding AC, assuming a haematocrit of 44% and an ACR of 100:6. The whole blood donations were 450 mL of whole blood.

Data Collection

Baseline data were collected through questionnaires and from the blood centre's database, LabCraft.

Blood Samples and Analyses

One tube of 6 mL EDTA plasma was collected non-fasting per participant immediately before the plasmapheresis procedure, at:

- Baseline week 1 (W1): Before the first donation in the study, after at least two months of no donation.
- End point week 18 (W18): Two weeks after the final donation.

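### The planned albumin mediation analysis has no safeguard on its non-randomised path, so shared variation in plasma volume can produce or inflate the mediated share

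*SAP*

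**What the plan says.** The mediation plan is a single sentence in the SAP's Statistical Analysis section: "We will also use mediation analyses to estimate the extent to which the effect is mediated through changes in albumin concentration". It is worded as a commitment, whereas the neighbouring alternatives (other distribution families, quantile regression) are only to be considered. It is not labelled exploratory.

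Under Variables, the mediator appears as "Plasma albumin concentration (as a mediator") with no sampling times. The outcome is "Difference in plasma concentrations between W1 and W18 of the following PFAS". The only independent variable listed is "Study group identity (HFPDs, RFPDs, control group").

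The Blood Samples and Analyses section gives two sampling points. Baseline is "Before the first donation in the study, after at least two months of no donation", and the second is "End point week 18 (W18): Two weeks after the final donation". The Introduction supplies the reason for looking at albumin: "PFAS are absorbed into the bloodstream and bind to proteins rather than fat".

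The SAP gives no mediation model, arm contrast, covariate or confounding assumption. Its only sensitivity analysis concerns values below the LOD, and that one is optional.

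**The concern.** A mediated share is the product of two paths. Randomisation protects the first, from group to albumin. It does not protect the second, from albumin to PFAS given group, which is an observational association between two changes.

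Both changes are changes in plasma concentration. If a donor's plasma is more dilute at W18 than at W1, both fall; if it is more concentrated, both rise. Plasma volume at sampling is thus a common cause of mediator and outcome. Ordinary variation between occasions is enough, and no acute effect of donation is needed. The resulting bias in the albumin coefficient is positive, the same sign that protein binding predicts, so a reader could take an artefact as confirmation of the mechanism.

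At stake is the statement of how much of the PFAS fall acts through albumin. The comparison of PFAS between randomised groups is not at stake.

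**Working it through.** The SAP states no figure on this point, so there is nothing to reproduce. The check asks how large the bias could be.

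**Inputs from the SAP.** Mediator and outcome are plasma concentrations; the two-sided significance level is 0.05; there are 96 + 122 = 218 samples. If every analysed donor gave two samples (an assumption), that is 218 / 2 = 109 pairs, or about 36 per arm.

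**Inputs assumed, not in the SAP.** Log scale; two arms; dilution SD s of 1% to 5% per draw; group effect on albumin of -0.03 to -0.10; total group effect on PFAS of -0.20; SD of other albumin change 0.04; SD of other PFAS change 0.10.

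**Model.** Let V be the change in log plasma volume, A the albumin change from other causes and θ the true effect of A on PFAS. The observed albumin change is A - V. The observed PFAS change is a direct group effect + θA - V + error. Within arms, the coefficient of PFAS change on albumin change tends to

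b = θ + (1 - θ)w, where w = var(V) / [var(V) + var(A)] and var(V) = 2s².

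The estimated share is (group effect on albumin) × b / (total effect).

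**No true albumin effect (θ = 0), so b = w.** At s = 3%: w = 0.0018 / (0.0018 + 0.0016) = 0.529. With a 6% albumin fall, the share is 0.06 × 0.529 / 0.20 = 16%. The same arithmetic gives:

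| s per draw | w | share, no fall | share, 3% fall | share, 6% fall | share, 10% fall |
|---|---|---|---|---|---|
| 0% | 0 | 0% | 0% | 0% | 0% |
| 1% | 0.111 | 0% | 1.7% | 3.3% | 5.6% |
| 2% | 0.333 | 0% | 5% | 10% | 17% |
| 3% | 0.529 | 0% | 8% | 16% | 26% |
| 5% | 0.758 | 0% | 11% | 23% | 38% |

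The column for no fall shows the necessary condition: b is biased, but without an arm difference in albumin the indirect effect averages zero.

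**How often both paths are significant.** This was simulated with 36 per arm and 4,000 runs per setting, testing each path at two-sided 0.05.
- No shared dilution, 6% fall: about 5%.
- s = 3%, no albumin difference by arm: about 3%.
- s = 1%, 6% fall: 7%.
- s = 3%, 6% fall: about 67%.
- s = 5%, 10% fall: over 99%.

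This frequency depends strongly on the assumed SD of other PFAS change. In the 3% and 6% case it drops from about 67% at SD 0.10 to about 24% at 0.20 and 13% at 0.30, while the average share stays near 16%. Doubling the SD of other albumin change to 0.08 lowers the share to about 6% and joint significance to about 27%.

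**True albumin effect not zero (s = 3%, 6% fall).** With θ = 0.5, the true share is 0.06 × 0.5 / 0.20 = 15%. The estimate uses b = 0.5 + 0.5 × 0.529 = 0.765, giving 0.06 × 0.765 / 0.20 = 23%. With θ = 1 (PFAS moving in proportion to albumin), b = 1 and the share is 30%, which is correct, so the bias is gone.

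**Does baseline adjustment help?** Adding baseline albumin and baseline PFAS to both models in the 3% and 6% case moved the simulated share only from about 15% to 14.5%, and joint significance from 69% to 60%. Dilution at W18 is still shared.

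**What a sensitivity analysis would show.** With θ = 0, the residual correlation that dilution induces, and at which the indirect effect reaches zero, is var(V) / √{[var(V) + var(A)] × [var(V) + 0.01]}. At s = 3% this is 0.0018 / √(0.0034 × 0.0118) = 0.28; at s = 2% it is 0.0008 / √(0.0024 × 0.0108) = 0.16.

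**The case against.** Several points on the other side stand.

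- **Shared dilution alone is not enough.** A reader might infer that it creates a mediated effect by itself. It does not: mean albumin must also differ between arms. With 24, 8 and 2 planned donations a difference is plausible, and mediation through albumin presupposes one, but the SAP does not show it.
- **The common sampling visits are inferred.** Only W1 and W18 are described and the mediator is a change, so the inference is reasonable. The timing may be set out in the protocol, which is not at hand.
- **Nothing says that plasma is dilute at W18.** That sample is taken two weeks after the last donation, which makes acute dilution less likely. The bias needs only ordinary variation between occasions, but its size is unknown.
- **A true albumin effect of zero is an extreme case.** The plan gives a binding rationale. For effects between zero and proportionality the bias inflates the share, and at proportionality it disappears.
- **Mediation is a minor part of the plan.** Albumin is listed among other variables, the objective compares donation groups, and no planned table reports mediation.

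These points limit the size and reach of the concern. They do not supply the missing safeguard: the plan still undertakes to estimate a causal quantity on an unprotected path.

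**Conclusion.** The concern holds in a limited form. As written, the mediation analysis can overstate how much of the donation effect on PFAS runs through albumin, because nothing addresses mediator-outcome confounding and plasma volume is an obvious shared component. This requires volume change that varies between donors, an arm difference in mean albumin, and a true PFAS response less than proportional to albumin.

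Over the assumed ranges, with no true albumin effect, the spurious share runs from about 2% in the mildest corner (about 3% with 1% dilution and a 6% fall) to 38% in the most severe. These figures are conditional on inputs that the SAP does not give, and no single rate of false-positive mediation should be quoted.

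The documents do not support the stronger readings that the trial will report false mediation, that albumin plays no part, or that the main results are compromised. This is a minor but inexpensive improvement.

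**What to change.** In the Statistical Analysis section of the SAP:

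1. State the visits at which albumin is measured and the arm contrast to be used.
2. Write out both models: W18 albumin on group, baseline albumin and baseline PFAS; and W18 PFAS on group, W18 albumin, baseline albumin and baseline PFAS. The baseline terms are for precision and do not remove the bias.
3. Report the indirect effect over a range of residual mediator-outcome correlations, with the correlation at which it reaches zero.
4. Label the mediation analysis exploratory, and state that the mediated share is not interpreted causally without that sensitivity result.

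I would not add a rule that suppresses the result when a modest correlation removes it. The cut-off would be arbitrary, and it could hide a genuine effect.

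The cost is a paragraph of SAP text and a few lines of Stata, with no new data if albumin is already available at both visits. The downsides are that the mediation result is stated less firmly, and that the sensitivity analysis cannot by itself separate dilution from true carriage by albumin.
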